1.1 Study design

This bridging study uses a randomized, double-blind, placebo-controlled, parallel-group design to assess the efficacy, safety, and tolerability of secukinumab 150 mg s.c. in Chinese participants with active PsA.

A screening period running up to 10 weeks before randomization will be used to assess participant eligibility followed by 52 weeks of treatment.

At BSL, approximately 40 Chinese participants whose eligibility are confirmed will be randomized to one of two treatment groups in 1:1 ratio:

- Group 1 – secukinumab 150mg s.c.:

Secukinumab 150 mg (1.0 mL PFS of 150 mg dose) administered at BSL, Weeks 1, 2, and 3 followed by dosing every four weeks starting at Week 4.

- Group 2 – placebo s.c.

Placebo (1.0 mL PFS) administered at BSL, Weeks 1, 2 and 3, followed by dosing every four weeks starting at Week 4.

At Week 16 the participants in Group 1 and Group 2 will be re-randomized in a blinded manner in 1:1 ratio separately.

- The participants in Group 1 will be re-randomized in 1:1 ratio to secukinumab 150 mg s.c. q4w regimen (1.0 mL PFS of 150 mg dose + 1.0 mL PFS of placebo) or secukinumab [REDACTED] s.c. q4w regimen ([REDACTED])
- The participants in Group 2 will be re-randomized in 1:1 ratio to secukinumab 150 mg s.c. q4w regimen (1.0 mL PFS of 150 mg dose + 1.0 mL PFS of placebo) or secukinumab [REDACTED] s.c. q4w regimen ([REDACTED])

Stratification is not applicable in the study.

A primary endpoint analysis was conducted after all participants complete Week 16 visit. Rescue medication was not allowed before the completion of Week 16 assessments (protocol Section 6.2.3). Although no participant will be restricted from receiving necessary rescue medications for lack of benefit or worsening of disease, if rescue with prohibited biologics (as described in section 6.2.2) occurs prior to completion of Week 16 assessments, participants will be discontinued from the study treatment. Efficacy will be assessed in detail at every study visit, and participants who are deemed not to be benefiting from the study treatment based upon safety

and efficacy assessments by the investigator, or for any reason of their own accord, are free to discontinue participation in the study at any time.

[figure not shown]
A follow-up visit will be done 12 weeks after last study treatment administration for all participants, regardless of whether they complete the entire study as planned or discontinue prematurely.

The total combined duration of treatment for this Phase III study is 52 weeks.

1.2 Study objectives and endpoints

Objective(s)	Endpoint(s)
Primary objective(s)	Endpoint(s) for primary objective(s)

To demonstrate the treatment effect of secukinumab 150 mg s.c. (q1w×4, followed by dosing q4w) in Chinese participants with active PsA is consistent with global population by assessing American College of Rheumatology 20 (ACR20) response rates in participants treated with secukinumab 150 mg s.c. compared to placebo s.c. at Week 16.	
ACR20 response at Week 16. A patient will be considered as improved according to the ACR20 criteria if he/she has at least 20% improvement in the three following measures:
Tender joint count;Swollen joint count;and at least 3 of the following 5 domains:
Patient's assessment of PsA painPatient's global assessment of disease activityPhysician's global assessment of disease activityHealth Assessment Questionnaire Disability Index (HAQ-DI©) scoreAcute phase reactant (hsCRP or ESR)
Secondary objective(s)	Endpoint(s) for secondary objective(s)

To evaluate the efficacy of secukinumab 150 mg s.c. (q1w×4, followed by dosing q4w) at Week 16 compared with placebo by assessing the proportion of participants achieving an ACR50 response.To evaluate the efficacy of secukinumab 150 mg s.c. (q1w×4, followed by dosing q4w) at Week 16 compared with placebo by assessing the changes from baseline in Disease Activity Score for 28 joints (DAS28-CRP).To evaluate the efficacy of secukinumab 150 mg s.c. (q1w×4, followed by dosing q4w) at Week 16 compared with placebo by assessing change from baseline in PASDAS (Psoriatic Arthritis Disease Activity Score).To evaluate the efficacy of secukinumab 150 mg s.c. (q1w×4, followed by dosing q4w) at Week 16 compared with placebo by assessing the changes	
ACR50 response rate at Week 16.Change from baseline in DAS28-CRP at Week 16.Change from baseline in PASDAS at Week 16.Change from baseline in SF36-PCS at Week 16.

Objective(s)	Endpoint(s)

from baseline in medical outcome short form health survey (SF36-PCS).
 
• To evaluate the efficacy of secukinumab 150 mg s.c. (q1w×4, followed by dosing q4w) at Week 16 compared with placebo by assessing the changes from baseline in Health Assessment Questionnaire - Disability Index (HAQ-DI©).• To evaluate the overall safety and tolerability of secukinumab 150 mg s.c. (q1w×4, followed by dosing q4w).	
• Change from baseline in HAQ-DI© at Week 16.• Physical examination, vital signs, laboratory values, AEs/SAEs.

2 Statistical methods

2.1 Data analysis general information

The primary endpoint analysis was performed after all participants complete Week 16. The Final analysis will be conducted when all participants have either withdrawn or completed the study. Any data analysis carried out independently by the investigator should be submitted to Novartis before publication or presentation.

Summary statistics for continuous variables will generally include the number of participants (N), mean, standard deviation (SD), minimum, lower quartile, median, upper quartile, and maximum. For binary or discrete variables, the absolute number of participants in each category and relative frequencies will be provided.

Unless otherwise specified, two-sided 95% confidence intervals will be displayed.

In case of a global health disruptive event, such as pandemic/epidemic (e.g., COVID-19), affecting the ability of the patient or the site to adhere to protocol requirements and assessments and therefore leading to a potential increase in the number of missing measurements, additional analysis populations may be defined as per the instructions and procedures outlined in Section 16.9 in the protocol.

The inferential efficacy evaluation of secukinumab relative to placebo was generally focus on the first 16 weeks of treatment unless otherwise specified.

Participants may be included in more than one treatment group for some analysis (e.g. exposure adjusted adverse events over the entire treatment period).

Note that the treatment groups for a participant may differ depending on the time period of the analysis and whether one assesses the participant for efficacy or safety.

Data may also be presented by a combination of the 'original' and 'switch' treatment groups. These treatment groups represent the treatment combinations the subjects experience over the course of the entire trial.

Efficacy data following re-randomization

Data will also be presented after Week 16, by a combination of the ‘original’ and ‘switch’ treatment groups and will be referred to as treatment sequence. These treatment sequences represent the treatment combinations the subjects experience over the course of the entire trial in case of re-randomization (refer to Section 2.1.1.1).

At the primary endpoint analysis, efficacy and safety data for the placebo-controlled period up to Week 16 were presented. Additional aspects of efficacy, safety and tolerability of secukinumab of the data collected up to the final database lock at the end of study will be investigated in the final analysis. Data collected after Week 16 will generally be summarized descriptively on the FAS population using treatment sequence.

2.1.1 General definitions

2.1.1.1 Treatment groups

In the final analysis, the summaries by treatment will be performed by the treatment sequence.

- Treatment sequence:

- AIN457 150 mg – AIN457 150 mg
- AIN457 150 mg – AIN457 [REDACTED]
- Placebo – AIN457 150 mg
- Placebo – AIN457 [REDACTED]

For some safety summaries (e.g., exposure-adjusted) the ‘switch’ treatment may be summarized separately:

- Entire study: Placebo, Any AIN457 150 mg, Any AIN457 [REDACTED], Any AIN457.

In the safety and efficacy listings, the groups will be presented by treatment sequence.

2.1.1.2 Study Day 1 and other study days

The first day of administration of randomized study treatment (first dose) is defined as Study Day 1 or Day 1.

All other study days will be labeled relative to Day 1. For event dates on or after Day 1, study day for a particular event date is calculated as [Date of event] – [Date of first dose] + 1, i.e., Day 2, Day 3, etc., will be one day, two days, etc., after Day 1, respectively. For the dates before Day 1, study day for an event date is calculated as [Date of event] – [Date of first dose], i.e., Day -1, Day -2, etc., will be one day, two days, etc., before Day 1, respectively. Duration of an event will be calculated as (Event end date – Event start date + 1).

The descriptor “Day 0” will not be used.

2.1.1.3 Screening, baseline and post-baseline definitions

Screening refers to any procedures (e.g., checking inclusion and exclusion criteria) performed prior to the date of first dose of study treatment (for safety analysis) or prior to the randomization date (for efficacy analysis). Per protocol, subject informed consent must be obtained prior to performing any study related activity. The date of signing informed consent is the start date of screening period. Any assessment obtained during the screening period will be labeled screening assessment. Assessments made on Day 1 may occur before or after the randomization or the first dose. Further information will be found in Programming Datasets Specifications (PDS).

For efficacy analyses, baseline is the last assessment (including unscheduled visits) obtained (on or) before randomization (day). All assessments obtained after randomization (day) are considered as post-baseline unless otherwise specified.

For safety analyses, baseline is the last assessment (including unscheduled visits) obtained (on or) before the first dose of study treatment. All assessments obtained after the first dose (day) of study treatment are considered as post-baseline unless otherwise specified.

Of note, baseline will be derived based on the randomization day or first dose day, exact randomization/dosing time is not considered.

In general, a baseline value refers to the last measurement made prior to administration of the first dose of study treatment. However, for patient reported outcomes, laboratory assessments and ECG if no pre-treatment value exists, values obtained after first dose of treatment can be used as baseline only if it was collected on the same day as first dose.

2.1.1.4 Day of last dose of randomized study treatment

The date of last dose will be collected via the electronic case report form (eCRF). The subject's exposure will be calculated considering the end of treatment period visit (e.g., treatment completion visit). If a subject discontinued early, then the last dose + 84 days or the last visit during the follow-up period whichever occurs earlier is considered.

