2.4 Treatments (study treatment, rescue medication, concomitant therapies, compliance)

2.4.1 Study treatment / compliance

The analysis of study treatment data will be based on the safety set. The number of visits with active and placebo injections received will be presented by treatment group.

The duration of exposure to study treatment will also be summarized by treatment group. In addition, the number and percentage of participants with cumulative exposure levels (e.g. any exposure, ≥ 1 week, ≥ 2 weeks, ≥ 3 weeks, ≥ 4 weeks, ≥ 8 weeks, etc.) will be presented.

Duration of exposure is defined as the time from first dose of study treatment to the time of treatment switch (for participants who switch treatment) or minimum of (last dose of the treatment + 84 days) and (last visit date). Participants who switch treatment during the study (e.g., from placebo to active treatment) will have exposure to both medications/doses using the appropriate start and stop dates.

Duration of exposure (years) = duration of exposure (days) / 365.25

Duration of exposure (100 subject years) = duration of exposure (years) / 100

The analysis of duration of exposure described above will be done for the entire study treatment period by treatment group.

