2.7.1 Adverse events (AEs)

Treatment-emergent adverse events (i.e., events started after the first dose of study treatment or events present prior to the first dose of study treatment but increased in severity based on preferred term and on or before last dose + 84 days) will be summarized.

Adverse events will be summarized by presenting, for each treatment group, the number and percentage of participants having any AE, having an AE in each primary system organ class and having each individual AE (preferred term). Summaries will also be presented for AEs by severity and for study treatment related AEs. If a participant reported more than one adverse event with the same preferred term, the adverse event with the greatest severity will be presented. If a participant reported more than one adverse event within the same primary system organ class, the participant will be counted only once with the greatest severity at the system organ class level, where applicable. Serious adverse events will also be summarized.

These summaries may be presented separately by placebo controlled period and entire study.

As appropriate, the incidence of AEs will be presented per 100 patient years of exposure (exposure-adjusted incidence rates).

Separate summaries will be provided for death, serious adverse event, other significant adverse events leading to discontinuation and adverse events leading to dose adjustment (including study treatment discontinuation).

A graphical display of relative frequencies within system organ classes and relative risks, as appropriate, will be presented.

Adverse events will also be reported separately by Standardized MedDRA Query (SMQ) according to MedDRA. The MedDRA version used for reporting the study will be described in a footnote.

Treatment emergent and non-treatment emergent adverse events will be listed.

Algorithms for date imputations will be provided in Programming Datasets Specifications.

For serious adverse events (SAEs) occurred during screening a listing were prepared for all subjects screened including screening failures at the primary endpoint analysis.

The safety analysis that will be performed for treatment emergent AEs and on treatment labs and vital signs for each analysis period is described in Table 2-1.

The data in the period of Day 1 – Week 16 were presented at the primary endpoint analysis; the data in the period of Entire treatment will be presented at the Final Analysis.

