Table 2-1 Overview of analysis on some safety endpoints

Analysis period	AEs & SAEs	AEs-SMQ	AEs by severity	study drug related AEs	notables for (vitals/ECG), lab criteria	Risk
Day 1 – Week 16	• crude incidence	• crude incidence	• crude incidence	• crude incidence	• crude incidence	• crude incidence
Entire Treatment	• crude incidence • exp.time adjusted incidence	• exp.time adjusted incidence	• crude incidence	• crude incidence	• crude incidence	• crude incidence • exp.time adjusted incidence

* Exposure-adjusted incidence rates will be done for the following:
At the PSOC for AE and SAE and Level 1 for Risks and SMQ analysis

For the legal requirements of ClinicalTrials.gov and EudraCT, two required tables on treatment emergent adverse events which are not serious adverse events with an incidence greater than 2% and on treatment emergent serious adverse events and SAE suspected to be related to study treatment will be provided by system organ class and preferred term on the safety set population.

If for a same patient, several consecutive AEs (irrespective of study treatment causality, seriousness and severity) occurred with the same SOC and PT:

- a single occurrence will be counted if there is ≤ 1 day gap between the end date of the preceding AE and the start date of the consecutive AE
- more than one occurrence will be counted if there is > 1 day gap between the end date of the preceding AE and the start date of the consecutive AE

For occurrence, the presence of at least one SAE / SAE suspected to be related to study treatment / non SAE has to be checked in a block e.g., among AE's in a ≤ 1 day gap block, if at least one SAE is occurring, then one occurrence is calculated for that SAE.

The number of deaths resulting from SAEs suspected to be related to study treatment and SAEs irrespective of study treatment relationship will be provided by SOC and PT.

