5.1 Visit window

5.1.1 Visit window

When visit windows are used, all visits will be re-aligned, i.e., they will be mapped into one of the visit windows. E.g., if the Week 4 visit of a subject is delayed and occurs on Day 46 instead of on Day 29, say, it will be re-aligned to visit window Week 8. In case of major deviations from the visit schedule, or due to unscheduled visits, several assessments of a subject may fall in a particular visit window (either scheduled or unscheduled). Statistical approaches to handle multiple assessments in a given visit window are specified in Table 5-2.

For lab/ECG/vital signs, as for follow-up (F/U) visits, only assessments that come as F/U nominal visit will be directly assigned as analysis F/U visit. Other assessments that are beyond the last on-treatment visit (Week 60) or after nominal F/U visit date will be listed under label “Week 60” in the listing.

For chemistry, hematology, urinalysis and lipids, the F/U visit will be presented in the summary table to present long-term safety of AIN. Of note, participants are allowed to have gaps in visits. All data collected will be displayed in listings.

Table 5-1 Analysis visit windows

Analysis visit	Target Day	Group 1	Group 2	Group 3	Group 4	Group 5	Group 6	Group 7	Group 8	Group 9
Baseline	1	≤ 1	≤ 1	≤ 1	≤ 1	≤ 1	≤ 1	≤ 1	≤ 1	≤ 1
Week 1	8	2-11						2-11		
Week 2	15	12-18						12-18		
Week 3	22	19-25						19-25		
Week 4	29	26-43		2-43	2-43	2-57		26-43		
Week 8	57	44-71		44-71	44-71			44-71	2-85	
Week 12	85	72-99	2-99	72-99	72-99	58-99		72-99		
Week 16	113	100-127	100-155	100-141	100-141	2-239	100-127	86-141	2-239	
Week 20	141	128-155						128-155		
Week 24	169	156-183		142-267	142-197	142-197		156-183	142-267	
Week 28	197	184-211	156-239					184-211		
Week 32	225	212-239			198-253	198-253		212-239		
Week 36	253	240-267						240-267		
Week 40	281	268-295	240-323		254-323	254-323		268-295		
Week 44	309	296-323						296-323		
Week 48	337	324-351						324-351		
Week 52	365	352-435	324-393	268-435	324-435	324-393	240-393	352-393	268-393	240-435

*The first administration of randomized study treatment (first dose) is defined as Day 1.

Group 1: ACR components, ESR, High sensitivity C-Reactive protein

Group 2: Hematology, blood chemistry, urinalysis

Group 3: SF-36 v2

Group 4: [REDACTED] [REDACTED] [REDACTED], Patient's global assessment of psoriasis and arthritis disease activity (VAS)

Group 5: Pregnancy test

Group 6: ECG, Body weight

Group 7: Vital signs

Group 8: Lipids

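### SAP 2.1.1.4 and 2.4.1 end a completer's exposure at different points (about Day 365 versus Day 421), and only 2.4.1 matches the adverse-event window

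*SAP*

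**What the plan says.** SAP 2.1.1.4, in the general definitions, says that a participant's "exposure will be calculated considering the end of treatment period visit (e.g., treatment completion visit". It then gives a separate rule: "If a subject discontinued early, then the last dose + 84 days or the last visit during the follow-up period whichever occurs earlier" is used.

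SAP 2.4.1 defines duration of exposure for everyone, from first dose to the time of "treatment switch (for participants who switch treatment) or minimum of (last dose of the treatment + 84 days) and (last visit date". It does not separate completers from discontinuers. It also converts the duration to years and to units of 100 subject-years.

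SAP 2.7.1 defines treatment-emergent events as those starting after the first dose, or present earlier "but increased in severity based on preferred term and on or before last dose + 84 days". It plans rates per 100 patient-years where appropriate. For the entire treatment period, Table 2-1 lists the exposure-adjusted rate beside crude incidence for AEs/SAEs and for Risks. For SMQs, as the table reads, it lists the adjusted rate alone. A footnote sets the level of these rates: "At the PSOC for AE and SAE and Level 1 for Risks and SMQ analysis".

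For some safety summaries, SAP 2.1.1.1 groups by treatment received ("Entire study: Placebo, Any AIN457 150 mg, Any AIN457", with one dose redacted). Otherwise the final analysis is by treatment sequence.

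**The concern.** The two sections agree for early discontinuers and at the Week 16 switch. They part only on the final treatment of a participant who completes. A completer's last visit is not Week 52: SAP 1.1 has everyone seen again 12 weeks after the last dose. So 2.4.1 carries exposure to that visit, while 2.1.1.4 appears to stop it at the end-of-treatment visit.

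The numerator follows 2.4.1. Adverse events (2.7.1), laboratory values (2.7.3), ECG (2.7.4.1) and vital signs (2.7.4.2) all run to last dose + 84 days. Imputation of adverse-event end dates (5.3.2) uses the same two limits as 2.4.1. If the 2.1.1.4 end point fed the rates, events in the last 8 weeks of follow-up would count while the matching person-time would not. Under the entire-study grouping this would raise the active-drug rates and leave placebo as it is.

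**Working it through.** **Inputs**
- Last planned dose at Week 48 (protocol Table 6-4).
- Protocol Table 8-1 days: Week 48 = 336, Week 52 = 364, F60 = 420.
- SAP Table 5-1 target days (Day 1 = first dose): Week 16 = 113, Week 44 = 309, Week 48 = 337, Week 52 = 365.
- Follow-up window 84 days; 365.25 days per year (SAP 2.4.1).
- Assumed: 40 participants, 10 in each of the four sequences, all on schedule.

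**Plan's own figure.** 336 + 84 = 420, the F60 day in Table 8-1. In SAP numbering, 337 + 84 = 421.

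**One completer**
- Whole study: 365 days (2.1.1.4) versus min(337 + 84, 421) = 421 days (2.4.1). Gap 56 days; 421/365 = 1.153.
- From the Week 16 switch: 365 − 113 + 1 = 253 versus 421 − 113 + 1 = 309 days; 309/253 = 1.221.
- Before the switch: 112 days under both rules.

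**Group totals if all 40 complete and attend F60**

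| Group | 2.4.1, days (patient-years) | 2.1.1.4, days (patient-years) | Ratio |
|---|---|---|---|
| Any AIN457 150 mg | 10 × (421 + 112 + 309) = 8,420 (23.1) | 10 × (365 + 112 + 253) = 7,300 (20.0) | 1.153 |
| Active regimen started at Week 16 | 20 × 309 = 6,180 (16.9) | 20 × 253 = 5,060 (13.9) | 1.221 |
| Any AIN457 | 20 × 421 + 20 × 309 = 14,600 (40.0) | 20 × 365 + 20 × 253 = 12,360 (33.8) | 1.181 |
| Placebo | 20 × 112 = 2,240 (6.1) | 2,240 (6.1) | 1.000 |

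The ratio is the inflation of the rate for a fixed event count. For example, 20 participants with an event in Any AIN457, without censoring time at the event, give 20/33.84 = 59.1 versus 20/39.97 = 50.0 per 100 patient-years. By treatment sequence the ratio is 421/365 = 1.153 in all four, so sequences are not biased against one another.

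**Sensitivity to discontinuation.** Suppose a share d stops in Treatment Period 2 with last dose at Week 32 (Day 225). Exposure then ends at 225 + 84 = Day 309 under both rules, which is 309 − 112 = 197 days from the switch. For Any AIN457 150 mg the ratio is [(1 − d)(421 + 309) + d(309 + 197) + 112] / [(1 − d)(365 + 253) + d(309 + 197) + 112]. At d = 5% this is 830.8/724.4 = 1.147.

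**Sensitivity to missed follow-up.** If a share m has no visit after Week 52, the excess is multiplied by (1 − m). For Any AIN457 150 mg at m = 10%: 1 + 0.9 × 0.153 = 1.138.

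| Assumption | Any 150 mg | Started at Week 16 | Any AIN457 |
|---|---|---|---|
| d = 5 / 10 / 20% | 1.147 / 1.140 / 1.127 | 1.213 / 1.204 / 1.185 | 1.174 / 1.166 / 1.150 |
| m = 10 / 25% | 1.138 / 1.115 | 1.199 / 1.166 | 1.163 / 1.136 |

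**Check within 2.1.1.4.** A participant who stops after the Week 44 dose and attends the 12-week visit is counted to 309 + 84 = Day 393. A completer, with one more dose, is counted to Day 365, which is 28 days less.

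**The case against.** The best defence is that the SAP already points to 2.4.1. That section alone formally defines the duration and converts it to the unit of the rates, and its handling of switchers reappears in the safety section (2.7). Section 2.1.1.4 sits under a heading about the last dose, is loosely worded and gives no formula. The Week 44 oddity arises only if the loose sentence is read as a hard stop, so it may count against that reading rather than as a second fault. The rate method may also be in redacted text: the SAP contents list shows redacted entries after 5.4, and the references include interval methods for Poisson means that no visible section uses.

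Much of this stands. Section 2.4.1 is the likelier choice of a careful programmer. But no visible sentence says that it governs, and the separate rule for early discontinuers in 2.1.1.4 has no purpose unless completers are treated differently.

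Support from SAP 5.1.1 is modest. It does refer to "Other assessments that are beyond the last on-treatment visit (Week 60", but as part of a listing rule, and protocol Table 8-1 places that visit in post-treatment follow-up.

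Sampling error would also exceed the artefact. An exact Poisson 95% interval runs from about −68% to +133% of the estimate for 5 events, and from −39% to +54% for 20. The error would overstate harm rather than hide it. Both facts limit the consequence, but neither reconciles the two sections.

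**Conclusion.** The concern holds. Two current, unredacted SAP sections give different exposure end points for completers, and only 2.4.1 agrees with the adverse-event window. The finding is this conflict, not a missing definition.

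The effect is conditional on 2.1.1.4 being the rule applied. With full completion, full F60 attendance and rare events, the ceilings are 15% for Any AIN457 150 mg, 22% for the regimen started at Week 16, 18% for Any AIN457 and 0% for placebo. Under the assumed 5–20% discontinuation they fall to 13–15%, 19–21% and 15–17%; with 10–25% missing F60, to 12–14%, 17–20% and 14–16%. If no visit follows Week 52 the gap is zero.

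Only exposure summaries and descriptive exposure-adjusted rates over the entire period are touched. Crude incidences, the Week 16 placebo-controlled comparison and the primary endpoint are not. No formal safety testing is planned, so no test result depends on it.

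**What to change.** Delete the exposure sentences from SAP 2.1.1.4 and replace them with a cross-reference to 2.4.1. State there, or in 2.7.1, that the 2.4.1 duration is the denominator for all exposure-adjusted rates, for completers and early discontinuers alike: to the treatment switch, or on the final treatment to the earlier of last dose + 84 days and last visit. If redacted text already names the denominator, check that it says the same. The cost is SAP wording only; no new data are needed.
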